MoA	Mechanisms of action
PAID	Problem Areas in Diabetes
PHQ-9	Patient Health Questionnaire-9
R&D	Research and Design
SAE	Serious adverse event
SAP	Statistical Analysis Plan
SD	Standard deviation
SDSCA	Summary of Diabetes Self-Care Activities Measure
SMI	Severe mental illness
SOP	Standard Operating Procedure
UoY	University of York
VIFs	Variance Inflation Factors
YTU	York Trials Unit

4 Design

Taken from the protocol: this study is a multi-centre, two-armed, parallel, individually randomised controlled trial with embedded process and economic evaluations. The two arms are the intervention plus standard care and standard care alone. The trial includes a 12-month internal pilot phase to assess recruitment assumptions and trial processes. The trial has a 22-month recruitment period (including the pilot). Follow up outcomes will be collected at 6 and 12-months post-randomisation.

5 Trial Objectives

The objectives of the trial are to investigate the clinical and cost-effectiveness of the DIAMONDS intervention for people with severe mental illnesses compared to usual care. The following are taken from the protocol.

- 1. To undertake a 12-month internal pilot to obtain estimates of recruitment and retention and to confirm trial viability.
- 2. To undertake a randomised parallel group comparison to determine the effects of the DIAMONDS intervention on glycated haemoglobin (HbA1c) at 12 months post-randomisation.
- 3. To undertake a randomised parallel group comparison to determine the effects of the DIAMONDS intervention on other outcomes related to physical health, psychological health and diabetes taken at 6 months and 12 months post-randomisation.
- 4. To conduct a detailed economic evaluation to assess the cost-effectiveness of the DIAMONDS intervention for both the trial period and the longer term (this will be presented elsewhere).
- 5. To conduct a process evaluation that will harness data form both qualitative and quantitative sources to address questions about whether the intervention was delivered as intended and how outcomes were produced. Additionally, the process evaluation will aim to identify barriers and enablers to post-trial implementation and scale-up, including whether the intervention can support self-management of other long-term conditions (LTCs) in people with severe mental illness (SMI).

6 Follow-up

Data will be collected at baseline, 6- and 12-month post-randomisation from participants.

		Baseline	6 months	12 months
	Demographics		monuns	montris
Age	Self-report	X	-	-
Sex	Self-report	X	-	-
		× ×	-	-
Ethnicity	Self-report		-	-
Index of Multiple Deprivation	Determined by study team	Х	-	-
(IMD)	based on participant's			
	postcode			
Type of SMI	Medical records	Х	-	-
Date diagnosed with SMI	Medical records	Х	-	-
Date diagnosed with diabetes	Medical records	Х	-	-
	Physical Health			
Height	Measured by study team	Х	Х	Х
Weight	Measured by study team	Х	Х	Х
BMI (calculated from height	Calculated by study team	Х	Х	Х
and weight)				
Waist circumference	Measured by study team	Х	Х	Х
Blood pressure	Measured by study team	Х	Х	Х
HbA1c	From central lab or medical	Х	Х	Х
records				
Total HDL and LDL cholesterol	From central lab or medical	Х	Х	Х
	records			

Table 1: Schedule of data collection

Triglycerides	From central lab or medical	х	х	х
	records			
Haemoglobin	From central lab or medical	Х	Х	Х
	records			
	Psychological health			
Brief Psychiatric Rating Scale	Self-report	Х	Х	Х
(BPRS)				
Patient Health Questionnaire-9	Self-report	Х	Х	Х
(PHQ-9)				
	Diabetes Measures			
Diabetes distress (PAID-5)	Self-report	Х	Х	Х
Summary of Diabetes Self-Care	Self-report	Х	Х	Х
Activities				
Smoking status	Self-report	Х	Х	Х
Physical activity (IPAQ)	Self-report	Х	Х	Х
Diabetes microvascular and	Medical records or self-report	Х	Х	Х
macrovascular compilations				
Urine albumin to creatinine	Medical records or self-report	х		х
ratio				
Amputation	Medical records or self-report	х		х
	Health economic outcomes			
Health-related quality of life	Self-report	Х	Х	Х
(EQ-5D-5L)				
Health resource use	Self-report	Х	Х	Х
	Process evaluation measures			
Mechanisms of Action*	Self-report	Х	Х	Х

*The Mechanisms of Action questions are also completed in a monthly CRF

7 Outcomes

7.1 Primary outcome(s)

The primary outcome of the main trial is glycated haemoglobin (HbA1c) at 12 months postrandomisation. It will also be measured at 6 months post randomisation as a secondary outcome. Participants who do not want a blood test can consent to their most recent routine blood test results being used if that test was taken between 6 weeks before and 6 weeks after the follow up date. This measure is collected in the bloods case report form (CRF).

7.2 Secondary outcome(s)

The following have been taken from the protocol:

Physical health

Cholesterol: Measured as part of a biochemical lipid profile (blood test) taken at the same time as the blood for the HbA1c measurement. Total cholesterol, LDL, HDL cholesterol, and triglycerides (all measured in mmol/L) will be recorded. These measures are collected in the bloods CRF.

Haemoglobin: Blood test taken at the same time as blood for HbA1c measurements and lipid profile. Haemoglobin will be recorded in g/L. **Body mass index (BMI):** Calculated using weight (kg) and height (metres) measurements using the following formula: *weight* (kg) / *height* (*metres*)². These measurements will be recorded in the investigator CRF.

Waist circumference: Measured following standard trust procedures and recorded in cm or inches. This measurement will be recorded in the investigator CRF.

Blood pressure: Systolic and diastolic blood pressure measured following standard trust procedure and recorded in mmHg. This measurement will be recorded in the investigator CRF.

Smoking status: Assessed through participant self-report: yes/no/never. This is recorded in the participant CRF.

Urinary albumin to creatinine ratio: Will be extracted from participants' medical records as a measure of diabetic nephropathy (this measure is only collected at baseline and Month 12).

Physical Activity: Physical activity will be measured using the International Physical Activity Questionnaire (IPAQ)(1). This instrument is a 7-item self-reported (short form) assessing physical activity in the last 7 days. Results will be reported in categories of activity levels (low, moderate, high).

In addition, we will provide all participants with wearable wrist accelerometers to obtain an objective measure of physical activity. Accelerometers will be given to participants at their baseline assessment and again at the six months follow-up time point, where they will be asked to wear the device continually for seven days. At the end of the seven-day period, they will be asked to return the device to the UoY team; this will be facilitated by the study team as needed. The University of York (UoY) team will carry out all data download and device set-up. The Research and Design (R&D) teams will receive instructions on how to activate the devices to start data collection.

Acceptability of wrist-worn accelerometers in this population has been confirmed in the STEPWISE study and the DIAMONDS feasibility study.

We will convert accelerometery data into activity profiles to assess time spent (a) in a sedentary state, (b) doing mild activity, or (c) doing moderate (or high) intensity activity.

Psychological health measures

Psychiatric symptoms: Assessed using the Brief Psychiatric Rating Scale (BPRS)(2). The BPRS assesses the level of 18 symptom constructs such as hostility, suspiciousness, hallucination, and grandiosity. Each symptom construct ranges from 1 (not present) to 7 (extremely severe). This measure is taken in the investigator CRF.

Depressive symptoms: Assessed using the Patient Health Questionnaire-9 (PHQ-9)(3). The questionnaire comprises nine items which are individually scored as 0 (not at all) to 3 (nearly every day) and then added to provide an overall score. The lower the overall score, the lower the severity of depression. This measure is taken in the participant CRF.

Diabetes measures

Diabetes distress: Assessed using the short form version of Problem Areas in Diabetes (PAID-5) scale (4), a validated self-report measure of diabetes distress. Each of the questionnaire's 5 items are measured on a five-point scale from 0 (not a problem) to 4 (a serious problem). Total scores on the PAID-5 can range from 0 to 20, with higher scores suggesting greater diabetes-related emotional distress This is measured in the participant CRF.

Summary of diabetes self-care activities: Assessed using the Summary of Diabetes Self-Care Activities Measure (SDSCA)(5). This tool contains 11 items, which measure the frequency of performing diabetes self-care activities over the last seven days. The respondent marks the number of days on which the indicated behaviour was performed using an eight-point Likert scale. These measures are taken in the participant CRF.

Insulin use: Assessed through participant self-report (yes/no) in the participant CRF.

Diabetes complications: Extracted from medical records or self-report.

- Microvascular: Retinopathy, Neuropathy, Nephropathy
- Macrovascular: Myocardial infarction, Peripheral vascular disease Nepthropathy, Stroke or Foot ulcers
- If amputation occurred

Quality of Life

Health-related quality of life: Assessed using the EQ-5D-5L, a validated self-report measure(6). This generic, validated, patient-reported outcome measure has five health domains (mobility; self-care; usual activities; pain/discomfort; and anxiety/depression) with five response options for each domain (no problems, slight problems, moderate problems, severe problems, and extreme problems). The scoring and more detailed analysis will be described as part of the health economic analysis plan.

Name	Score Range	Description	Score calculation	How missing items will be handled	Interpretation of score
IPAQ	MET minutes: 0-	7-item self-report questions assessing physical activity in the past 7 days.	MET minutes is the sum of the MET minutes of each category. Each MET minutes category is calculated by taking the number of minutes doing a category of activity multiplied by that category's constant. Each category is limited to 180 minutes of activity per day. Those constants are: Walking = 3.3 Moderate activity = 4 Vigorous activity = 8	No guidance is provided. MET minutes will only be calculated if all items are present.	 High: Vigorous activity for at least 3 days, achieving at least 1500 MET minutes OR 7 days of any activity achieving at least 3000 MET minutes. Moderate: 3 or more days of vigorous activity/walking for at least 30 minutes a day OR 5 or more days of moderate activity/walking for at least 30 minutes a day OR 5 or more days of any activity, achieving at least 600 MET minutes. Low: Any other amount of activity.
BPRS	18-126	Assesses the level of 18 psychiatric symptoms, each range from 1 (not present) to 7 (extremely severe)	Sum the scores.	No guidance is provided by developers; however, we will accept up to 4 items to be missing. If so an average of completed items can be imputed for the missing items	Direction of positive effect: Increase <31: Not significantly ill 31-40: Mildly ill 41-50: Moderately ill >51: Markedly ill Direction of positive effect: Decrease
PHQ-9	0-27	Comprises nine items measuring depressive symptoms, each scored as 0 (not at all)	Scoring: scores are summed for a total.	No guidance is provided by developers however, we will allow up to 2 items to be missing. If so, an average of	0 = No or minimal depression 27 = Severe depression

Table 2: Summary of scoring methods and score interpretation for instruments used in the DIAMONDS trial

PAID-5	0-20	to 3 (nearly every day). 5 items measured on a scale from 0 (not a problem) to 4 (a serious problem)	Scoring: scores are summed to generate a score out of 20.	completed items can be imputed for the missing items. No guidance is provided by developers. As there are only 5 items, scores will only be calculated if all items are	Direction of positive effect: Decrease Direction of positive effect: Decrease
		measuring diabetes distress.		completed.	
SDSCA	0-7 (except smoking status which is 0 or 1 and the number of cigarettes smoked)	11 items measuring frequency of diabetes self-care activities. Each item is measured on an eight-point Likert scale.	Scoring: Scores are calculated for five categories. General diet: mean of items 1 and 2 Specific diet: reverse the value of item 4 (0=7, 1=6,), then take the mean of items 3 and 4 Exercise: mean of items 5 and 6 Blood-Glucose Testing: mean of items 7 and 8 Foot-Care: mean of items 9 and 10 Smoking status: item 11 and number of cigarettes per day	No guidance is provided by developers. Due to the small number of items within each category, all items within a category must be present for that category to be scored.	Direction of positive effect: Increase

Health resource use

A bespoke health resource use questionnaire that has been tested in the feasibility study and refined in line with feedback received will be used to collect participants' use of primary care, secondary care and community-based services over a six-month period. This measure is taken in the participant CRF. These measures will be used as part of the health economic evaluation, the planned analysis for which will be presented separately.

Mechanisms of Action

We will quantitatively collect information about the mechanisms of action (MoAs) used in the DIAMONDS intervention. The 'Change One Thing' app has built-in monthly reviews of MoAs that participants will work through with their DIAMONDS Coach at their 1-to-1 sessions. In addition, we will use a set of self-report process measures at baseline and follow-up. The mechanisms of action data are collected using a bespoke MoA CRF.

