Not reported	
Total cholesterol	
Ν	
Mean (SD)	
Median (IQR)	
Not reported	
LDL cholesterol	
Ν	
Mean (SD)	
Median (IQR)	
Not reported	
HDL cholesterol	
Ν	
Mean (SD)	
Median (IQR)	
Not reported	
Haemoglobin	
Ν	
Mean (SD) DIAMONDS Statistical A	

DIAMONDS Statistical Analysis Plan version 1 Page | 21

Physical Health		Total
Median (IQR)		
Not reported		

	Intervention	Control	Total
IPAQ			
Low physical activity			
(mins/week)*			
n (%)			
Mean (SD)			
Median (IQR)			
Min, Max			
Not reported			
Moderate physical activity			
(mins/week)			
n (%)			
Mean (SD)			
Median (IQR)			
Min, Max			
Not reported			
Vigorous physical activity			
(mins/week)			
n (%)			
Mean (SD)			
Median (IQR)			
Min, Max			
Not reported			
Total physical activity (MET-			
mins/week)*			
n (%)			
Mean (SD)			
Median (IQR)			
Min, Max			
Not reported			
IPAQ score categories, n (%)*			
Number with data			
Low			
Moderate			
High			
Not reported			
Sedentary activity			
(mins/weekday)			
n (%)			
Mean (SD)			
Median (IQR)			
Min, Max			
Not reported			
BPRS			
BPRS total score (range 18-			
126)			
•		1	1

	Intervention	Control	Total
n (%)			
Mean (SD)			
Not reported			
BPRS total score Group, n (%)			
Number with data			
No symptoms (≤ 24)			
Mildly ill (25-32)			
Moderately ill (33-49)			
Markedly ill (50-69)			
Severely ill (70-89)			
Extremely ill (≥90)			
Not reported			
PHQ-9			
PHQ-9 score (range 0-27)			
n (%)			
Mean (SD)			
Not reported			
PHQ-9 Score Group, n (%)			
Number with data			
No Depression (≤4)			
Mild Depression (5-9)			
Moderate Depression (10-			
14)			
Moderately Severe			
Depression (15-19)			
Severe Depression (20-27)			
Not reported			
PAID-5			
PAID-5 score (range 0-20)			
n (%)			
Mean (SD)			
Not reported			
Participants in high distress, n			
(%) Number with data			
Not in high distress (PAID			
score <8)			
High distress (PAID score ≥8)			
Not reported			
SDSCA (scores represent			
number of days 0-7)			
General Diet Score (days)			
n (%)			
Mean (SD)			
Median (IQR)			
Not reported			
Specific Diet Score (days)			
n (%)			

	Intervention	Control	Total
Mean (SD)			
Median (IQR)			
Not reported			
Exercise Score (days)			
n (%)			
Mean (SD)			
Median (IQR)			
Not reported			
Blood-Glucose Testing Score			
(days)			
n (%)			
Mean (SD)			
Median (IQR)			
Not reported			
Foot Care Score (days)			
n (%)			
Mean (SD)			
Median (IQR)			
Not reported			
Smoked in the last 7 days, n			
(%)			
Number with data			
Yes			
No			
Not reported			

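### Table 2 gives walking two different day thresholds for the IPAQ Moderate category, and its BPRS severity bands disagree with those in appendix Table 3

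*SAP*

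**What the plan says.** **IPAQ.** The scoring table in SAP section 7.2 (Table 2) gives three alternative routes to Moderate. The first two read "3 or more days of vigorous activity/walking for at least 30 minutes a day OR 5 or more days of moderate activity/walking", and the five-day route carries the same 30-minute minimum as the three-day route. The third is "5 or more days of any activity, achieving at least 600 MET minutes". The residual category is "Low: Any other amount of activity". The MET constants are 3.3 for walking, 4 for moderate and 8 for vigorous activity. Section 7.2 reports the result as low, moderate or high, and section 12.9 places IPAQ levels among the outcomes described by arm without a model.

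**BPRS.** Table 2 gives the interpretation "<31: Not significantly ill 31-40: Mildly ill 41-50: Moderately ill >51: Markedly ill". The baseline outcome shell in section 16 (appendix Table 3) has six groups for the same total: up to 24, 25–32, 33–49, 50–69, 70–89, and 90 or more. Its third group, for instance, is "Moderately ill (33-49" inclusive. The SAP does not say which set governs. Table 2 also allows up to four missing BPRS items, filled with the mean of the completed items. Section 12.9 models the BPRS as a continuous score.

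**The concern.** A scoring table should let two programmers produce the same output from the same data. Two features of this one work against that.

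First, when two routes are joined by OR and share an activity and a daily duration, the one asking for more days adds nothing for that activity. The five-day threshold for walking was presumably meant to do something, and for people whose only activity is walking it does nothing. IPAQ category is a listed secondary outcome, and walking is a plausible behaviour for a self-management intervention to change. Where the Low/Moderate line falls for walkers therefore affects what the by-arm table shows.

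Second, the same BPRS total receives a different severity label depending on which table is followed. The baseline severity profile of the sample would then depend on a choice the SAP has not made. Section 10 says the statisticians do not stay blind, which is a further reason to settle such choices in the document rather than during programming.

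**Working it through.** The plan states no figure for these rules, so there is none to reproduce. The check applies the rules as written. All inputs come from Table 2 in section 7.2 and appendix Table 3.

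**IPAQ, walking only, 30 minutes a day.** MET-minutes = days × 30 × 3.3. The slash is read as 'or' in both clauses.

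| Walking days | MET-minutes | Three-day route | Five-day route | 5 days and 600 MET-min | As written | Walking only through five-day routes |
|---|---|---|---|---|---|---|
| 2 | 198 | no | no | no | Low | Low |
| 3 | 297 | yes | no | no | Moderate | Low |
| 4 | 396 | yes | no | no | Moderate | Low |
| 5 | 495 | yes | yes | no | Moderate | Moderate |
| 6 | 594 | yes | yes | no | Moderate | Moderate |
| 7 | 693 | yes | yes | yes | Moderate | Moderate |

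Every row that meets the five-day route already meets the three-day route. The two versions of the rule part at 3 and 4 days.

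**Where the five-day route still works.** Take two walking days and three days of moderate activity, 30 minutes each: 2 × 30 × 3.3 + 3 × 30 × 4 = 198 + 360 = 558 MET-minutes. With no vigorous activity this fails the three-day route (only two walking days) and the 600 MET-minute route, and it is Moderate only through the five-day route. The same holds for five or more days of moderate activity alone, at 30 minutes a day, whenever 600 MET-minutes is not what decides. The redundancy is therefore confined to patterns with three or more walking days.

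**BPRS.** Eighteen items scored 1 to 7 give totals from 18 to 126, which is 126 − 18 + 1 = 109 integer values. The lowest band of each table is treated as equivalent, although the wording differs.

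| Total | Table 2 | Appendix Table 3 | Number of totals |
|---|---|---|---|
| 25–30 | not significantly ill | mildly ill | 6 |
| 33–40 | mildly ill | moderately ill | 8 |
| 50 | moderately ill | markedly ill | 1 |
| 51 | no band (41–50, then above 51) | markedly ill | 1 |
| 70–126 | markedly ill | severely or extremely ill | 57 |

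Sum: 6 + 8 + 1 + 1 + 57 = 73 of 109. Over 18–69 alone it is 6 + 8 + 1 + 1 = 16 of 52.

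**Non-integer totals.** With k items missing and mean imputation, total = sum of completed items × 18 / (18 − k). For k = 1 and a sum of 38, this is 38 × 18 / 17 = 40.2, which lies between 31–40 and 41–50 in Table 2. For k = 1 and a sum of 31, it is 31 × 18 / 17 = 32.8, between 25–32 and 33–49 in appendix Table 3. Over all 376 combinations of k = 1 to 4 and possible sum, 7 have no band in Table 2 and 14 have none in the appendix.

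**The case against.** The best case against acting is that nothing inferential depends on either rule. The BPRS enters a mixed model as a total score, and the shell for estimated effects (appendix Table 9) lists only that score. IPAQ levels are only described. BPRS groups appear as table rows only in the baseline shell, and Table 2's bands are interpretive notes. All of this stands and sets the scale of the point.

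Several stronger readings are tempting, and the SAP does not support them:

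- **The five-day route never decides any case.** It does, for moderate activity alone and for mixes with fewer than three walking days, such as the 558 MET-minute example.
- **Participants will be misclassified.** That presupposes a known correct rule. The SAP shows a redundancy and a conflict between tables. It cannot show which BPRS band set is right, and its source for the IPAQ scoring is cited, not reproduced.
- **The Moderate routes are wrong because their MET totals differ.** They are alternatives, two of them defined by days and minutes, and nothing requires equal MET totals. Three vigorous days of 30 minutes give 3 × 30 × 8 = 720. The figure of 297 only illustrates where the overlap bites.
- **The missing-item rule deletes computable scores.** Table 2 says "MET minutes will only be calculated if all items are present", while the formula uses only walking, moderate and vigorous activity. However, the seven items are not listed. A sitting item is only inferred from the sedentary row in appendix Table 3, and complete-item scoring is a stated choice that PAID-5 scoring shares.

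Accelerometer data give another view of activity, with baseline-adjusted group differences. They are collected at baseline and 6 months only, so they do not replace the IPAQ at 12 months.

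**Conclusion.** The point holds in a limited form. For people whose only activity is walking, the five-day threshold has no effect, and those walking 30 minutes on 3 or 4 days are Moderate where a five-day rule would make them Low. This rests on reading the slash as 'or', the natural reading and the same in both clauses. How many participants are affected cannot be known from the SAP.

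The BPRS band sets are incompatible: 72 integer totals carry different labels, and one more, 51, has no label in Table 2. The 57 totals from 70 upwards make up most of that count, and the SAP does not say how often scores fall there. The count measures disagreement between the rules, not an expected share of participants.

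The consequence is confined to IPAQ levels by arm and the baseline BPRS groups. The primary analysis, the BPRS total-score model and the other modelled secondary outcomes do not change. It is still worth correcting: one rule defeats part of itself, and the other leaves a planned table undetermined.

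**What to change.** 1. **IPAQ.** Check the Moderate definition against the scoring rules of the cited instrument and give walking a single day threshold. The internal logic points to taking walking out of the three-day route, since the five-day route then regains its function, but the source should confirm this.
2. **BPRS bands.** Choose one band set, cite its source, and use it in both Table 2 and appendix Table 3, with every total from 18 to 126 assigned, including 51.
3. **BPRS imputation.** State how non-integer totals are banded, for example by rounding before banding or by defining bands with continuous cut-points.
4. **Optional.** State whether MET minutes need only the walking, moderate and vigorous items.

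The cost is a few wording edits in the scoring table and one in the appendix shell, entered in the SAP amendment log. No new data, no change to any model and no effect on sample size.
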